### **9.2.1 Study stopping rules**

#### **Treatment arm stopping rules**

If any of the following events occur, all ongoing treatment arms sharing the same suspect drug(s) will be placed on hold to further enrollment, and no new participants may be dosed, however dosing of those without safety concerns may continue. In addition, a full review of all available clinical safety data and discussion with the investigators will take place.

- One participant on study drug experiences any adverse event that is CTCAE Grade 4 or higher that is suspected to be related to study drug(s)
- Two participants on study drug experience a similar adverse event that is a CTCAE Grade 3 or higher other than ALT elevation regardless of whether the events are suspected to be related to study drug(s)
- Two participants are discontinued due to a liver event as defined in [Section 16.1](#)
- Two participants are discontinued due to a renal event as defined in [Section 16.2](#)

- Two participants meet the same individual participant stopping rule 6, 7, or 8 ([Section 9.1.1](#))
- One participant experiences any adverse event that is CTCAE Grade 5 regardless of whether the event is suspected to be related to study drug(s)
- One participant experiences an SAE that is suspected to be related to study drug(s)
- The Principal Investigator and Sponsor consider that the number and/or severity of adverse events justify discontinuation of the suspect drug(s)
- The Sponsor unilaterally requests it

Safety reviews for treatment arm stopping will be conducted cooperatively between medically qualified representatives of the sponsor and investigator and a joint decision will be made. The treatment arm may resume following the safety review, if the investigator and sponsor agree it is safe to proceed.

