If the elevation is confirmed, close observation of the participant will be initiated, including consideration of treatment interruption or discontinuation (as described in [Table 16-1](#)) if deemed appropriate, close monitoring, causality and clinical evaluation should be performed as below:

- Repeating the liver tests to confirm elevation as described in [Table 16-1](#).
- Discontinuation of the investigational drug, if appropriate. Note that discontinuation is mandatory in the case of decompensated cirrhosis as defined by ascites, bleeding esophageal varices, hepatic encephalopathy, jaundice or any other liver decompensation related symptom.
- Hospitalization of the participant, if appropriate.
- An investigation of the liver event which needs to be followed until resolution, such as by:
  - Obtaining a more detailed history of symptoms and prior or concomitant diseases.
  - Obtaining a history of concomitant drug use (including nonprescription or over-the-counter medications and herbal and dietary supplement preparations), alcohol use, recreational drug use, and special diets.
  - Excluding acute viral hepatitis Types A, B, C, D, and alcoholic hepatitis; hypoxic/ischemic hepatopathy; autoimmune hepatitis and biliary tract disease.
  - Imaging such as abdominal US, CT or MRI, as appropriate.
  - Obtaining a history of exposure to environmental chemical agents.
  - Considering gastroenterology or hepatology consultations.
  - Conducting pathology and serology tests, and/or liver biopsy, based on investigator's discretion.

Participants who permanently discontinue study drug due to potential liver toxicity must be followed for close monitoring until abnormalities stabilize to baseline levels or baseline grade of abnormality and the participant is asymptomatic.

All follow-up information, and the procedures performed must be recorded on the appropriate CRFs, including SAE forms when appropriate.

The baseline value will be calculated as the mean of the last two assessments before first administration of the study drug.

**Table 16-1 Management of Participants with Confirmed ALP, ALT, AST, or Bilirubin Elevations With or Without Liver Related Clinical Symptoms**

Baseline	Treatment-Emergent (Confirmed a )	Liver-Related Clinical Symptoms b	Action taken	
			Monitoring c	Study Drug
ALT and/or AST				

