Baseline ALT and/or AST < 2 × ULN	ALT and/or AST > 3 × ULN but ≤ 5 × baseline	None Present	Laboratory monitoring and causality evaluation Comprehensive clinical evaluation and laboratory monitoring, as well as causality evaluation d , and PK sampling	Continue dosing Interrupt dosing e
	ALT and/or AST > 3 × ULN but ≤ 5 × ULN AND total bilirubin > 2 × ULN (in Gilbert's syndrome, see footnote f )	With or without liver-related clinical symptoms	Comprehensive clinical evaluation and laboratory monitoring, as well as causality evaluation d , and PK sampling	Interrupt dosing e
	ALT and/or AST > 3 × ULN and > 5 × baseline	With or without liver-related clinical symptoms	Comprehensive clinical evaluation and laboratory monitoring, as well as causality evaluation d , and PK sampling	Permanently discontinue
Baseline ALT and/or AST ≥ 2 × ULN	ALT and/or AST > 2 × baseline but ≤ 3 × baseline	None Present	Laboratory monitoring and causality evaluation Comprehensive clinical evaluation and laboratory monitoring, as well as causality evaluation d , and PK sampling	Continue dosing Interrupt dosing e
	ALT and/or AST > 2 × baseline but ≤ 3 × baseline AND total bilirubin > 2 × ULN f	With or without liver-related clinical symptoms	Comprehensive clinical evaluation and laboratory monitoring, as well as causality evaluation d , and PK sampling	Interrupt dosing e
	ALT and/or AST > 3 × baseline	With or without liver-related clinical symptoms	Comprehensive clinical evaluation and laboratory monitoring, as well as causality evaluation d , and PK sampling	Permanently discontinue
Baseline normal or elevated ALT and/or AST values	ALT and/or AST > 3 × ULN and > 2 × baseline AND either total bilirubin > 2 × baseline OR INR increase by >0.3 to a value >1.5	With or without liver-related clinical symptoms	Comprehensive clinical evaluation and laboratory monitoring, as well as causality evaluation d , and PK sampling	Interrupt dosing e
ALP				

Baseline	Treatment-Emergent (Confirmed a )	Liver-Related Clinical Symptoms b	Action taken	
			Monitoring c	Study Drug
Baseline ALP ≤ ULN	ALP > 1.5 × ULN  (not due to known bone pathology)	None	Laboratory monitoring and causality evaluation c	Continue dosing

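### Liver Table 16-1 puts a participant whose baseline ALT and AST straddle 2 × ULN in both of its blocks, and for a defined band of rises the two blocks give opposite dosing actions

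*Protocol*

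**What the plan says.** Table 16-1 in Protocol Section 16.1 sets the action for confirmed liver enzyme rises according to baseline. The two ALT/AST blocks are:

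- **Lower block**, headed "Baseline ALT and/or AST < 2 × ULN". For "ALT and/or AST > 3 × ULN but ≤ 5 × baseline" the action is continue dosing without liver symptoms and interrupt dosing with them. For "ALT and/or AST > 3 × ULN and > 5 × baseline" it is permanently discontinue, whatever the symptoms.
- **Higher block**, headed "Baseline ALT and/or AST ≥ 2 × ULN". For "ALT and/or AST > 2 × baseline but ≤ 3 × baseline" the action is again continue without symptoms, interrupt with them. For "ALT and/or AST > 3 × baseline" it is permanently discontinue, whatever the symptoms.

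Further rows call for interruption when bilirubin or INR criteria are also met. On baseline, Section 16.1 says: "The baseline value will be calculated as the mean of the last two assessments before first administration of the study drug".

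Section 9.1.1 sends liver events to Section 16.1 for the decision to stop treatment. Section 9.2.1 holds enrolment in every ongoing arm sharing the suspect drug when "Two participants are discontinued due to a liver event as defined in" Section 16.1.

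**The concern.** The two blocks look intended to divide participants by baseline. The and/or in both headings means that they do not. One enzyme below 2 × ULN satisfies the first heading and one at or above it satisfies the second, so a participant with one of each satisfies both. The two blocks have different discontinuation thresholds (5 × and 3 × baseline), so the same confirmed result can meet rows with opposite actions.

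The table decides individual discontinuation in a trial whose primary objective is safety and whose entry criteria require raised ALT. The discontinuation count also feeds the arm hold. That route matters because the Section 9.2.1 rule on two similar Grade 3 events leaves out ALT elevation, and item 8 of Section 9.1.1 leaves out liver events. Two sites reading different blocks could count the same case differently. Both Cohort 1 arms contain LYS006, so if that is the suspect drug the count bears on both.

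**Working it through.** No figure in the plan needs reproducing; this is a check of decision logic. Values are multiples of ULN. Write *b* for an enzyme's baseline and *x* for its confirmed on-treatment value. The symptom rows are merged in the text available; I read them as two rows (none, present), as the ALP part of the table sets them out.

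**1. Who is in both blocks.** Lower: ALT < 2 or AST < 2. Higher: ALT ≥ 2 or AST ≥ 2. Both hold exactly when one enzyme is below 2 and the other is not. With both enzymes on the same side, only one block applies. Straddling baselines are admissible: Section 5.1 sets a minimum for ALT and none for AST, and Section 5.2 (criterion 21) caps both at 5 × ULN.

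**2. Where the actions clash.** Lower block, continue or interrupt: 3 < *x* ≤ 5*b*. Higher block, permanently discontinue: *x* > 3*b*. Both hold when max(3, 3*b*) < *x* ≤ 5*b*. For *b* ≥ 1 the band runs from 3 to 5 times baseline. For *b* between 0.6 and 1 it is narrower, because 3 × ULN becomes the lower limit. For *b* ≤ 0.6 it is empty, since 5*b* ≤ 3.

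**3. Examples (no symptoms; bilirubin and INR criteria not met).** Each rise is 4 × baseline.

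| Baseline ALT, AST | Rise | Lower block | Higher block | Each enzyme by its own baseline | Participant by the higher enzyme |
|---|---|---|---|---|---|
| 2.5, 1.2 | AST to 4.8 | 4.8 > 3 and ≤ 6.0: continue | 4.8 > 3.6: discontinue | continue | discontinue |
| 1.5, 2.5 | ALT to 6.0 | 6.0 > 3 and ≤ 7.5: continue | 6.0 > 4.5: discontinue | continue | discontinue |
| 2.5, 1.2 | ALT to 10.0 | 10.0 > 3 and ≤ 12.5: continue | 10.0 > 7.5: discontinue | discontinue | discontinue |

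In the first two rows the two sensible ways of classifying give different actions. In the third they agree, and the clash arises only if a low AST is used to place a high-baseline ALT in the lower block. With symptoms, continue becomes interrupt in every row.

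**4. Outside the band.** Take baseline ALT 2.5 with a straddling AST. At 2.5 × (6.25) and 3 × baseline (7.5) both blocks say continue. At 5.1 × (12.75) both say discontinue. An enzyme at 0.9 rising 3.3-fold to 2.97 meets no lower-block row because it stays below 3 × ULN, yet meets the higher block's discontinuation row. The blocks still differ there, but it is not the continue-versus-discontinue clash.

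**5. Is there a tie-break?** The text of Section 16.1, footnotes a to g, Section 9.1.1 and Section 9.2.1 contain no per-enzyme rule and no order of precedence. Footnote e mentions the permanent discontinuation criteria only as a limit on restarting after an interruption. The ALP and total bilirubin blocks do not have this problem, since each divides a single analyte at ULN.

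**The case against.** The strongest reply is that a row should be read with the same enzyme throughout: and/or then means whichever enzyme is raised, and its own baseline selects the block. On that reading each result has one block and the overlap disappears. It is a natural reading, and it disposes of the third example. But the protocol does not state it, and classifying the whole participant by the higher enzyme is also sensible and gives the other action in the first two examples.

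The second reply is that a site does not act on the table alone. Section 16.1 requires re-evaluation within 48 to 72 hours and sponsor notification within 48 hours, and leaves room for judgement about interruption or discontinuation. Section 9.1.1 requires stopping on several safety grounds that do not depend on the table. Section 9.2.1 allows a hold on investigator and sponsor judgement or at the sponsor's request, and the Safety Assessment Committee (Section 10.2.1) reviews the arms. This stands and lessens the consequence. None of it says which row governs or how the case is counted.

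It is also true that no endpoint or model uses the block and that laboratory values and adverse events are reported either way. The decision still reaches the analysis indirectly: SAP Section 6 drops most efficacy assessments from the day of treatment discontinuation.

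Two stronger readings are not supported. A reader might infer that any enzyme rise in a straddling participant receives contradictory instructions; step 4 shows that the clash is confined to one band. A reader might also infer that a sizeable part of the roughly 50 Cohort 1 participants would be affected. The documents give neither the joint distribution of baseline ALT and AST nor a rate of such rises. Straddling baselines alone would in any case not be a count of conflicts, because a confirmed rise within the band is also needed.

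**Conclusion.** Wrong as written. The headings of the two ALT/AST blocks overlap for any participant with one enzyme on each side of 2 × ULN. In that group, a confirmed rise above 3 × and up to 5 × the enzyme's own baseline that also exceeds 3 × ULN meets rows with opposite actions: continue (or interrupt, with symptoms) against permanently discontinue. Bilirubin or INR rows may apply as well.

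The conclusion rests on the literal headings, on the absence of any assignment or precedence rule in the visible text, and on reading the merged symptom entries as two rows. Its size can be stated only as that band; no frequency or headcount can be derived. Existing judgement and notification steps make it a matter of clear instruction and consistent counting, not evidence that participants would go unprotected. It should be corrected because the rule decides discontinuations and feeds a hold triggered by only two of them.

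**What to change.** Reconcile the two ALT/AST blocks in Table 16-1 so that each enzyme result falls in exactly one. State:

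- whether the baseline class is assigned by enzyme or by participant;
- which row prevails when a result meets two, including the bilirubin and INR rows;
- that the same rule is used to count liver-event discontinuations for Section 9.2.1.

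Which classification and which action are right is for the sponsor's clinical team; this point takes no view. The cost is a wording change at the next amendment, with no additional tests, visits or data.

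### Liver safety Table 16-1 can attach two different dosing actions to one laboratory pattern, partly because one row is cut at 5 × ULN among rows cut at 5 × baseline, and it states no order of precedence

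*Protocol*

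**What the plan says.** All of this is in Protocol Section 16.1, Table 16-1, unless noted.

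Stratum "Baseline ALT and/or AST < 2 × ULN":
- "ALT and/or AST > 3 × ULN but ≤ 5 × baseline": continue without liver symptoms, interrupt with them. No bilirubin condition is stated.
- "ALT and/or AST > 3 × ULN but ≤ 5 × ULN", together with total bilirubin above 2 × ULN: interrupt, whatever the symptoms.
- "ALT and/or AST > 3 × ULN and > 5 × baseline": permanently discontinue, whatever the symptoms.

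Stratum "Baseline ALT and/or AST ≥ 2 × ULN": the first row and the bilirubin row both run from 2 to 3 × baseline, and "ALT and/or AST > 3 × baseline" means permanent discontinuation.

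Any baseline: "ALT and/or AST > 3 × ULN and > 2 × baseline", together with bilirubin above 2 × baseline or a defined INR rise: interrupt. This row has no upper limit.

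The bilirubin block says interrupt when total bilirubin exceeds 2 × ULN in a participant whose baseline bilirubin is not above ULN.

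Footnote e allows restart after an interruption only for participants who do not meet the permanent discontinuation criteria, and only if the interruption lasted less than 10 days. No sentence says which row governs when more than one is met.

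Protocol Section 9.2.1 places all arms sharing the suspect drug on enrolment hold if "Two participants are discontinued due to a liver event as defined in" Section 16.1.

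**The concern.** In the upper stratum every limit that separates the rows is a multiple of baseline, and the rows meet at 3 × baseline. In the lower stratum one of the three rows switches to a multiple of ULN. Its upper edge therefore meets the start of the discontinuation row only when baseline equals ULN exactly. The uncapped any-baseline row adds a second overlap that has nothing to do with this switch.

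The table is operative. Protocol Sections 6.5.1 and 9.1.1 both send liver-related dosing decisions to Section 16.1. If two rows with different actions apply, two sites can act differently on the same results. The classification also feeds the arm-level rule, where the trigger is only two participants, so a single different classification can matter. Both Cohort 1 arms contain LYS006 (Section 17.1), so a hold attributed to that drug would reach both. The arm rule for two similar Grade 3 or higher events sets ALT elevation aside, which leaves more of the work for ALT signals to the liver-discontinuation count.

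**Working it through.** The plan gives no figure to reproduce. The check codes the rows as inequalities. Let b be the baseline and x the confirmed on-treatment value of the same enzyme, both in multiples of ULN. Participants with emerging Gilbert's syndrome (footnote f) are set aside.

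| Row | ALT/AST condition | Further condition | Action |
|---|---|---|---|
| A (b < 2) | 3 < x ≤ 5b | none stated | continue; interrupt if symptoms |
| B (b < 2) | 3 < x ≤ 5 | bilirubin > 2 × ULN | interrupt |
| C (b < 2) | x > 3 and x > 5b | none | discontinue |
| D (b ≥ 2) | x > 3b | none | discontinue |
| E (any b) | x > 3 and x > 2b | bilirubin > 2 × baseline, or INR rise | interrupt |

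**Step 1: B against C.** Both apply when max(3, 5b) < x ≤ 5. That band is non-empty only if 5b < 5, that is, b < 1.
- b = 0.6: 5 × 0.6 = 3.0, so the shared band is 3 to 5 × ULN, the whole of row B.
- b = 0.8: 5 × 0.8 = 4.0, so the shared band is 4 to 5 × ULN, half of row B. For example, x = 4.5 satisfies 4.5 ≤ 5 and 4.5 > 4.0.
- b = 1.0: 5 × 1.0 = 5.0, so there is no overlap.

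**Step 2: can b < 1 occur?** The ALT entry minimum is 43 IU/L (males) or 28 IU/L (females) (Section 5.1). The laboratory's ULN is not in the documents. Assuming it is the top of the normal range in Table 4-1, the minima are 43/33 = 1.30 and 28/25 = 1.12 × ULN, so ALT at the entry minimum is above 1 × ULN. ALT would get below it if the laboratory ULN exceeds 43 or 28 IU/L respectively, or if the two pre-dose values averaged for the liver baseline fall below ULN. AST has only a ceiling of 5 × ULN (Section 5.2, criterion 21) and no minimum, so b < 1 is open to AST.

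**Step 3: E against C and D.**
- For b < 2, any x in row C exceeds 3, and it exceeds 2b because 5b > 2b.
- For b ≥ 2, any x in row D exceeds 3b, which is at least 6, so it exceeds both 3 and 2b.

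Every value in a discontinue row therefore meets the ALT/AST part of row E. Once the bilirubin or INR condition is also met, both actions apply, at any baseline. For example, with b = 1.5 and x = 8, 8 > 5 × 1.5 = 7.5 gives row C, and 8 > 3 with 8 > 2 × 1.5 = 3.0 gives row E.

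**Step 4: 1 < b < 2, bilirubin > 2 × ULN, no symptoms.** Values with 5 < x ≤ 5b have left row B and have not reached row C. At b = 1.5 this is 5 to 7.5 × ULN. Row A applies and says continue. Two other places say interrupt:
- The bilirubin block applies because Section 5.2, criterion 21 excludes total bilirubin above ULN, so baseline bilirubin should not exceed ULN.
- Row E normally applies as well, since x > 5 exceeds 2b (below 4), and bilirubin above 2 × ULN exceeds 2 × baseline when baseline bilirubin is at or below ULN.

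**The case against.** The strongest reply is that interruption and discontinuation both stop dosing at once and differ only in whether restart is possible. Footnote e closes restart to anyone who meets the discontinuation criteria, restart also requires consultation with the sponsor, and the sponsor is notified within 48 hours. This largely stands for the individual participant. It leaves the precedence to be inferred, and it does not say how such a participant is counted in Section 9.2.1. The 10-day limit narrows the difference further, because an interrupted participant who has not recovered in time cannot restart either.

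It can also be said that row A is meant only for participants without raised bilirubin. The upper stratum supports that reading, since its first and bilirubin rows cover the same range. On that reading the conflict in Step 4 disappears, but the table does not state the condition.

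Two stronger readings are tempting and are not supported:
- **Values in Step 4 fall in no row.** They do not. Row A and the bilirubin block both cover them, and normally row E does too. This is a conflict between rows, not a gap.
- **The drop in the discontinuation level at a baseline of 2 × ULN is an error.** The level is 5 × 1.9 = 9.5 × ULN at b = 1.9 and 3 × 2.0 = 6.0 × ULN at b = 2.0. Section 16.1 describes a process adapted to participants with altered liver function, and different multiples in different baseline strata are a clinical design choice. A step at the boundary follows from it and contradicts nothing.

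Finally, Section 9.2.1 has other triggers, such as one related serious event or one related Grade 4 event. A hold therefore need not turn on this count.

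**Conclusion.** The inconsistency is real but limited. Three conflicts follow from the table's own text:
- Row B overlaps row C for baselines below 1 × ULN. This is mainly an AST matter, and it also requires bilirubin above 2 × ULN.
- The uncapped any-baseline row overlaps both discontinue rows at any baseline. This does not depend on the mix of references.
- A continue row stands against interrupt rows for symptom-free participants with a baseline of 1 to 2 × ULN, if row A is read without an unstated bilirubin condition.

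The statement that ALT at its entry minimum lies outside the first conflict rests on taking the top of the Table 4-1 range as the ULN. A reader might infer that the overlap will change an arm-hold decision. The documents give no frequency for these patterns, so the defensible claim is only that the count is not uniquely defined for participants who meet two rows. That is worth correcting in a table that governs dosing and feeds a two-participant trigger.

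**What to change.** Three changes to the Protocol:
1. In Table 16-1, stratum below 2 × ULN, reconcile the limit of the bilirubin row with those of the rows above and below it. If the first row is meant to apply only when bilirubin is not raised, say so.
2. Add a sentence to Section 16.1 stating which action prevails when a participant meets more than one row, including the any-baseline row and the bilirubin block.
3. State in Section 9.2.1, by cross-reference, how such a participant is counted for the arm-level rule.

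Which thresholds and which order of precedence are right is for the sponsor and its liver safety experts. The cost is an amendment to one table and two sentences. Sample size, assessment schedule and planned statistical analyses are unaffected.

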## 16.2 Appendix 2: Renal safety monitoring

Recommended actions and follow-up assessments regarding renal function data are shown in [Table 16-2](#). If evaluation of a renal event reveals a reversible etiology not related to study drug, the study drug may be restarted as long as the period of interruption is less than 10 days.

Note that the day to day variability of a particular participant's serum creatinine is reflected in the different values measured at screening versus baseline. Because of this, the investigator should use the higher of these two values as the reference against which to compare on-treatment serum creatinines.

